Page 1 of 70

# **1 GLOSSARY OF TERMS**

Name of Test product(s)	ORA System with VerifEye+
Name of Test Product(s)	Alcon Toric Calculator (Barrett)
Adverse Device Effect	Adverse event related to the use of an investigational medical device (test product) or control product. Note: This definition includes adverse events resulting from insufficient or inadequate instructions for use, deployment, implantation, installation, or operation; any malfunction; and use error or intentional misuse of the test product or control product.
Adverse Event	Any untoward medical occurrence, unintended disease or injury, or untoward clinical signs (including abnormal laboratory findings) in subjects, users or other persons, whether or not related to the investigational medical device (test product). Note: For subjects, this definition includes events related to the test product, the control product, or the procedures involved. For users or other persons, this definition is restricted to events related to the test product. Requirements for reporting Adverse Events in the study can be found in Section 11.
Anticipated Serious Adverse Device Effect	Serious adverse device effect which by its nature, incidence, severity, or outcome has been identified in the risk management file.
Device Deficiency	
 
Inadequacy of a medical device with respect to its identity, quality, durability, reliability, safety, or performance. Note: This definition includes malfunctions, use errors, and inadequate labeling.
 
Requirements for reporting Device Deficiencies in the study can be found in Section 11.
 

**Document:** TDOC-0055329 **Status:** Effective

Enrolled Subject	Any subject who signs an informed consent form for participation in the study.
Interventional Clinical Trial	A research trial that prospectively assigns, whether randomly or not, human participants or groups of humans to one or more health-related interventions to evaluate the effects on health outcomes, and/or a research trial in which diagnostic or monitoring procedures beyond standard of care are conducted and generate outcomes for use in analysis of data.
Investigational Product	Is defined as a preventative (vaccine), a therapeutic (drug or biologic), device, diagnostic, or palliative used as a test or control product in a clinical trial, including a product with a marketing authorization when used or assembled (formulated or packaged) in a way different from the authorized form, or when used for an unauthorized indication, or when used to gain further information about the authorized form.
Malfunction	Failure of a medical device to perform in accordance with its intended purpose when used in accordance with the instructions for use or clinical investigation plan.
Non-serious Adverse Event	Adverse event that does not meet the criteria for a serious adverse event.
Postmarketing/Post- authorization study	Any study conducted within the conditions laid down in product labelling and other conditions laid down for the marketing of the product or under normal conditions of use. A postmarketing study falls either within the definitions of an interventional or a non- interventional study and may also fall within the definition of a post-approval study.
Product Complaints	Any oral, electronic, or written communication that alleges deficiencies related to the identity (labeling), quality, durability, reliability, safety, effectiveness, or performance of a marketed product, including failure of the product, labeling or packaging to meet specifications, whether or not

**Document:** TDOC-0055329 **Status:** Effective Version: 5.0; Most-Recent; Effective; CURRENT

	the product is related to or caused the alleged deficiency. A complaint may allege that an adverse event or medical device malfunction has occurred.
Randomized Subjects	Any subject who is assigned a randomized treatment.
Serious Adverse Device	Adverse device effect that has resulted in any of the
Effect (SADE)	consequences characteristic of a serious adverse event.
Serious Adverse Event	Adverse event that led to any of the following:
(SAE)	
 
Death.
 
A serious deterioration in the health of the subject that either resulted in:
 

	a. a life-threatening illness or injury. Note: Life-threatening means that the individual was at immediate risk of death from the event as it occurred, ie, it does not include an event which hypothetically might have caused death had it occurred in a more severe form.
	b. any potentially sight-threatening event or permanent impairment to a body structure or a body function.

	c. in-patient hospitalization or prolonged
	hospitalization.
	Note: Planned hospitalization for a pre-
	existing condition, without serious
	deterioration in health, is not considered a
	serious adverse event. In general,
	hospitalization signifies that the individual
	remained at the hospital or emergency ward
	for observation and/or treatment (usually
	involving an overnight stay) that would not
	have been appropriate in the physician's office
	or an out-patient setting. Complications that
	occur during hospitalization are adverse
	events. If a complication prolongs
	hospitalization or fulfills any other serious
	criteria, the event is serious. When in doubt as
	to whether "hospitalization" occurred, the
	event should be considered serious.
	d. a medical or surgical intervention to prevent
	a) or b).
	e any indirect harm as a consequence of
	incorrect diagnostic test results when used
	within manufacturer's instructions for use
	• Fetal distress, fetal death, or a congenital
	abnormality or birth defect.
	Refer to Section 11 for additional SAEs.
Serious Public Health	Any event type which results in imminent risk of death
Threat	serious deterioration in state of health, or serious illness that
	requires prompt remedial action. This would include: Events
	that are of significant and unexpected nature such that they
	become alarming as a potential public health hazard, eg,
	human immunodeficiency virus (HIV) or Bird Flu.

**Document:** TDOC-0055329 **Status:** Effective Version: 5.0; Most-Recent; Effective; CURRENT

Unanticipated Serious	Serious adverse device effect which by its nature, incidence,
Adverse Device Effect	severity or outcome has not been identified in the risk
(USADE)	management file.
Use Error	Act or omission of an act that results in a different medical
	device response than intended by manufacturer or expected
	by user. Note: This definition includes slips, lapses, and
	mistakes. An unexpected physiological response of the
	subject does not in itself constitute a use error.

Page 11 of 70

# 2 LIST OF ACRONYMS AND ABBREVIATIONS

Table 2–1	List of Acronyms	and Abbreviations	Used in This Protocol
-----------	------------------	-------------------	------------------------------

Abbreviation	Definition
AAS	All-Implanted Analysis Set
ADE	Adverse device effect
AE	Adverse Event
BCDVA	Best Corrected Distance Visual Acuity
BSS	Balanced salt solution
CFR	Code of Federal Regulations
CRF	Case Report Form
D	Diopter
DEP	Deviations and Evaluability Plan
DEQ	Defocus equivalent
DFU	Directions for use
EBMD	Epithelial basement membrane dystrophy
eCRF	Electronic case report form
EDC	Electronic data capture
EN	European Standard
ETDRS	Early Treatment Diabetic Retinopathy Study
FDA	Food and Drug Administration
GCP	Good Clinical Practice
GPCMS	Global Product Complaint Management System
HIV	Human immunodeficiency virus
ICF	Informed consent form
ICH	International Council for Harmonisation of Technical Requirements
	for Pharmaceuticals for Human Use
IEC	Independent ethics committee
IOL	Intraocular Lens
IP	Investigational product
IRB	Institutional review board
ISO	International Organization for Standardization
LCD	Liquid crystal display
LogMAR	Logarithm of the minimum angle of resolution
mm	Millimeter

**Document:** TDOC-0055329 **Status:** Effective

Page 12 of 70

Abbreviation	Definition
mmHg	Millimeter of mercury
МОР	Manual of procedures
N/A	Not applicable
ORA	Optiwave Refractive Analysis
OVD	Ophthalmic viscosurgical device
PI	Principal Investigator
PPS	Per Protocol Analysis Set
SADE	Serious adverse device effect
SAE	Serious Adverse Event
SD	Standard Deviation
SIA	Surgically induced astigmatism
SOP	Standard operating procedure
SS	Safety Analysis Set
SSI	Secondary surgical intervention
US	United States
USADE	Unanticipated serious adverse device effect
VA	Visual acuity
YAG	Yttrium-aluminum-garnet

# **3 PROTOCOL SUMMARY**

Investigational	Devices
product type	
Study type	Interventional
Investigational	Investigational Products:
products	The ORA System with VerifEye + is made up of the following components:
	The ORA System Aberrometer is mounted on a compatible surgical microscope. It measures optical aberrations which are converted to wavefront data to generate refraction data. The refraction data is used for selecting the power of an intraocular lens (IOL). Once a toric IOL is placed in the eye, the aberrometer indicates when the toric marks of the IOL are aligned with the intended axis. A key feature of ORA with VerifEye + is that surgical information is displayed through the microscope oculars.
	The Cart provides control and power to, and receives and processes data from, the aberrometer. The portable cart is tethered to the ORA System via a cable.
	The LCD Touchscreen is mounted on the cart and displays operating screens for user input, option selections, and data output. It can also display wavefront analyses.
	The Alcon Toric IOL Calculator (Barrett) is a tool to assist the treating ophthalmic surgeon in selecting a Toric IOL for adult patients with corneal astigmatism undergoing cataract removal. Accurate keratometry and biometry measurements are required to achieve optimal visual outcomes.
	The calculator offers two options with the manufacturer's model specific A-constant for IOL calculation:
	1. Barrett Toric Calculator algorithm which calculates a patient-specific effective lens position and also

	
 
estimates the effect of posterior corneal astigmatism. Optimum outcomes are achieved with a centroid Surgically Induced Astigmatism (SIA) value.
 
Holladay I Vergence formula which calculates a patient-specific effective lens position, but does not consider posterior corneal astigmatism.
 

	The Calculator combines patient specific biometry data and the
	planned surgery information to recommend a Toric IOL model
	with the optimal anglinent axis within the capsular dag.
Purpose and	The Alcon Toric Calculator (Barrett) is a modern IOL calculator
rationale	that includes estimates of the posterior corneal astigmatism in the
	selection of the IOL power.
	The ORA System with VerifEye + is an intraoperative device that measures the total corneal astigmatism in the aphakic condition which is used for IOL power selection. Also, in the pseudophakic condition, ORA provides guidance for alignment of the Toric axis mark.
	These modern technologies account for the posterior corneal astigmatism in the IOL power selection and this study is intended to evaluate the visual acuity outcomes when they are used for implantation of a Toric IOL.
Objective(s)	Primary Effectiveness:
	To evaluate the percentage of eyes with best corrected distance visual acuity (BCDVA) of 20/20 or better in eyes implanted with AcrySof ® Toric selected by ORA with VerifEye + and Barrett Toric Calculator

Page 15 of 70 Safety: To evaluate adverse events including secondary surgical interventions related to the investigational device. Endpoint(s) Primary Effectiveness: Percentage of eyes with BCDVA of 20/20 or better at 6 months

**Document:** TDOC-0055329 **Status:** Effective

	Safety:
	1. Adverse events including secondary surgical
	interventions related to the investigational device
	2. Device deficiencies
Assessment(s)	Effectiveness
	Monocular Best Corrected Distance Visual Acuity in logMAR
	Safety
	Adverse Events
	Device Deficiencies
Study Design	This is a prospective, randomized, contralateral, multicenter,
	achieve 90 evaluable subjects. Treatments will be randomized
	between eyes and the eye with the more visually significant
	cataract, as measured by best corrected distance visual acuity
	(BCDVA), will undergo surgery first. If the BCDVA is equal
	between eyes, me fight eye will undergo surgery first.

	The Barrett Toric Calculator via the Alcon Toric Calculator will be used for IOL power selection preoperatively. Sites that have LenSx will use it for primary and secondary incisions, capsulorhexis, and phacofragmentation consistently in both eyes for all subjects. Sites that don't have LenSx will use standard manual procedures. For the eyes in the ORA with VerifEye + study group, the IOL power and axis and axis mark alignment will be provided by ORA. For eyes in the Barrett Toric study group, the IOL power and axis will be provided by the Barrett Toric Calculator and axis alignment will be done manually (ie, without ORA guidance).
	The study will be conducted at up to 10 sites in the US. Surgery will be done on each eye on different days 7 to 14 days apart. Total follow-up duration is 6 months. There will be 10 visits in total. Refer to the Overview of Study Procedures Table for an overview of the visit schedule and the assessments to be performed at each visit.
Subject population	Subjects who require cataract surgery and a Toric IOL in both eyes. Subjects will be required to have preoperative keratometric astigmatism of 0.75 D to 3.00 D and require the AcrySof IQ ® Toric SN6AT3 – 6 as determined by Alcon Toric Calculator.
Key inclusion criteria (See Section 8.1 for a complete list of inclusion criteria)	
 
Inclusion Criteria:
 
1. 22 years of age or older
 
2. Preoperative keratometric astigmatism of 0.75 to 3.00 D
 
3. Planned implantation of AcrySof IQ Toric SN6AT3 – T6 as determined by the Alcon Toric Calculator
 
4. Potential postoperative visual acuity of 0.04 logMAR (20/20) or better
 

**Document:** TDOC-0055329 **Status:** Effective

	5. Willing and able to complete all required postoperative
	visits
	6. Able to comprehend and sign the informed consent form
Key exclusion	Exclusion Criteria:
criteria	
(See Section 8.2 for a	1. Unclear intraocular media other than cataract
complete list of	2. Axial length $< 21.5$ and $> 27.0$ mm
avaluaion aritaria)	3. Significant irregular corneal astigmatism as measured by a
exclusion cinterna)	1 Unstable tear film per Investigator judgement
	5 Significant anterior or posterior segment disease
	6. Prior intraocular or corneal surgery
	7. Prior retinal detachment
	8. Pregnancy or lactation, current or planned, during the course of the study
	
 
9. Participation in another concurrent clinical trial per the PI indgement
 

	
 
10. Presence or history of any condition or finding that makes the subject unsuitable as a candidate for cataract surgery or study participation or may confound the outcome of the study, in the opinion of the Investigator.
 

	Exclusion Criteria During Surgery
	
 
Intra-op complications such as but not limited to posterior capsular tear, wound burn and need to place a suture
 
ORA or Alcon Toric Calculator recommends an IOL other than AcrySof IQ Toric SN6AT3-T6
 

Data analysis and	No formal statistical hypothesis testing is planned in support of the
sample size	primary objective Rather the data will be summarized using
justification	descriptive statistics by treatment group.
	There will be two effectiveness analysis sets. The All Implanted
	Analysis Set (AAS) includes all eyes with successful IOL
	implantation, T3-T6 and recommended by ORA. The Per Protocol
	Analysis Set (PPS) includes all eyes with successful IOL
	implantation, T3-T6 and recommended by ORA and with no major
	protocol deviations. The primary analysis set for effectiveness is the PPS.

	• $20/32$ Snellen or better: $\leq 0.24 \log MAR$
	• 20/40 Snellen or better: $\leq 0.34 \log MAR$
	In addition, descriptive statistics including sample size, mean, median, standard deviation, number of subjects/eyes, minimum, maximum and (two-sided) 95% confidence interval will be presented.
	Descriptive statistics for adverse events (including SSIs) will be presented for study eyes. The rates of all adverse events will be provided with counts and percentages, and these rates will be accompanied by two-sided exact 95% confidence intervals.
	In order to estimate the percent of eyes with BCDVA of 20/20 or better (ie, $\leq 0.04 \log$ MAR) at 6 months postop, the 95% confidence interval for the percent of eyes with BCDVA of 20/20 or better at 6 months postop will be calculated based on the binomial distribution. With a sample size of 90 eyes, per the binomial distribution, the width of the 95% confidence interval ranges from 4.0% to 21.5%. As an example, for an observed outcome of 70%, the 95% confidence interval per binomial distribution is (59.4%, 79.2%) with a width of 19.8%.
Key words	ORA, Verifeye+, Barrett, Toric, IOL

Alco Docu Statu	n - B ment: s: Effec	usiness Use Only Proto TDOC-0055329 tive	col - Cl Versi	inical	.0; Most	-Recent	; Effec	tive; CU	JRRENT	Eff	ective D	22
		Early Exit		x	x						$\mathbf{X}^{+}$	_
		Visit 5A Day 120 – 180 days Post Visit 00A		x	x						$\mathbf{X}^{+}$	
	Both eyes	Visit 4A Day 80 – 100 days Post Visit 00A		x	x						$\mathbf{X}^{+}$	_
		Visit 00Å										

Printed By:

# Schedule of Study Procedures and Assessments

	Both eyes	1 st	Operative E	ye	2 nd Operative Eye Both eyes						
	Visit 0 Day -30 to 0 Preoperative	Visit 00 Day 0 Operative	Visit 1 Day 1-2 Post Visit 00	Visit 2 Day 7-14 Post Visit 00	Visit 00A 7-14 days Post Visit 00	Visit 1A Day 1-2 Post Visit 00A	Visit 2A Day 7-14 days Post Visit 00A	Visit 3A Day 30-45 days Post Visit 00A	Visit 4A Day 80 – 100 days Post Visit 00A	Visit 5A Day 120 – 180 days Post Visit 00A	Early Exit
Informed Consent	х										
Demographics	х										
Medical, ocular history	х	х	х	х	х	х	х	х	х	х	х
Concomitant Medications	х	х	х	х	х	х	х	х	х	х	х
Inclusion/Exclusion	х	х			Х						
Urine Pregnancy Test	х										
Monocular Best Corrected Distance Visual Acuity	х			х			х	х	$\mathbf{X}^{+}$	$\mathbf{X}^{+}$	$\mathbf{X}^{+}$

Page **21** of **70** 

Document: TDOC-0055329	Alcon - Business Use Only
Version: 5.0; Most-Recent; Effective:	Protocol - Clinical

Document: TDO Status: Effective Both 2nd Operative Eye 1st Operative Eye Both eyes eyes 7-14 days Post Visit 00 Day 80 - 100 days Post Day 7-14 Post Visit 00 Day 1-2 Post Visit 00A Day 1-2 Post Visit 00 Day 30-45 days Post Visit 00A Day 120 – 180 days Post Visit 00A Day 7-14 days Post Visit 00A Day 0 Operative Day -30 to 0 Preoperative Early Exit Visit 00A Visit 00 Visit 3A Visit 4A Visit 00A Visit 1A Visit 5A Visit 0 Visit 1 Visit 2 Visit 2A Preoperative IOL selection with Alcon х Toric Calculator Cataract Surgery Х Х х Lens Information Х ORA measurement Х х including reticle orientation, aphakic

Status: Effective	Document: TDOC-0055329	Alcon - Business Use Only
	Version: 5.0; Most-Recent; Effective; CURRENT	Protocol - Clinical

	Both eyes	1 st	Operative E	ye	2 nd Operative Eye		Both eyes				
	Visit 0 Day -30 to 0 Preoperative	Visit 00 Day 0 Operative	Visit 1 Day 1-2 Post Visit 00	Visit 2 Day 7-14 Post Visit 00	Visit 00A 7-14 days Post Visit 00	Visit 1A Day 1-2 Post Visit 00A	Visit 2A Day 7-14 days Post Visit 00A	Visit 3A Day 30-45 days Post Visit 00A	Visit 4A Day 80 – 100 days Post Visit 00A	Visit 5A Day 120 – 180 days Post Visit 00A	Early Exit
capture, pseudophakic capture											
Adverse events	Х	Х	Х	Х	X	Х	X	Х	Х	Х	X
Device Deficiencies		Х	Х	х	Х	Х	Х	х	х	х	х

# Page 23 of 70

## Page 24 of 70

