# **12 ANALYSIS PLAN**

# **12.1 Subject Evaluability**

The final subject evaluability will be determined using the Deviations and Evaluability Plan (DEP) prior to locking the database.

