# 12.7 Interim Analyses and Reporting

There is one interim analysis in this study. The objective of the interim analysis is to assess the effectiveness and safety of each treatment group when all subjects complete Visit 3A (30-60 days post Visit 00A).

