# **14 ETHICS**

This clinical study must be conducted in accordance with the ethical principles contained within:

- The Declaration of Helsinki, and in compliance with the ICH E6 GCP Consolidated Guideline, ISO 14155:2011, and the applicable US FDA 21 CFR Regulations.
- SOPs of the Study Sponsor and contract research organizations participating in the conduct of the clinical study and all other applicable regulations.
- Notifications and timelines for reporting protocol deviations should be based upon applicable Ethics Committee requirements

The Investigator must ensure that all personnel involved in the conduct of the study are qualified to perform their assigned responsibilities through relevant education, training, and experience. The Investigator and all clinical study staff must conduct the clinical study in compliance with the protocol. Deviations from this protocol, regulatory requirements and/or GCP must be recorded and reported to the Sponsor prior to database lock. If needed, corrective and preventive action should be identified, implemented, and documented within the study records. Use of waivers to deviate from the clinical protocol is prohibited.

Before clinical study initiation, this protocol, the informed consent form, any other written information given to subjects, and any advertisements planned for subject recruitment must be approved by an IRB/IEC. The Investigator must provide documentation of the IRB/IEC approval to the Study Sponsor. The approval must be dated and must identify the applicable protocol, amendments (if any), informed consent form, assent form (if any), all applicable recruiting materials, written information for subject, and subject compensation programs. The IRB/IEC must be provided with a copy of the Package Insert, any periodic safety updates, and all other information as required by local regulation and/or the IRB/IEC. At the end of the study, the Investigator must notify the IRB/IEC about the study's completion. The IRB/IEC also must be notified if the study is terminated prematurely. Finally, the Investigator must report to the IRB/IEC on the progress of the study at intervals stipulated by the IRB/IEC.

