1.2 Study Description

This is a prospective, randomized, contralateral, multicenter, postmarket study. A total of 115 subjects will be enrolled to achieve 90 evaluable subjects. Treatments will be randomized between eyes and the eye with more visually significant cataract as measured by BCDVA will undergo surgery first. If the BCDVA is equal between eyes, the right eye will undergo surgery first.

The IOL power will be determined using any IOL power calculator. Sites that have LenSx will use it for primary and secondary incisions, capsulorhexis, and phacofragmentation consistently in both eyes for all subjects. Sites that don't have LenSx will use standard manual procedures.

For the eyes in the ORA with VerifEye + study group, the IOL toric power and axis and axis mark alignment will be provided by ORA. For eyes in the Barrett Toric study group, the IOL toric selection and axis will be provided by the Barrett Toric Calculator and axis alignment will be done manually (ie, without ORA guidance).

The study will be conducted at up to 10 sites in the US. Surgery will be done on each eye on different days 7 to 14 days apart. Total follow-up duration is 6 months. There will be 10 visits in total. The study flow chart is available in Figure 7-1 of the protocol, and schedule of study procedures and assessments are available in Table 3-1 of the protocol.

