4.6 Interm Analysis for Effectiveness

The interim analysis will be conducted to summarize the following endpoints:

• Percentage of eyes with BCDVA of 20/20 or better at 1 month

•	

There will be an interim database lock and the interim analysis will be conducted after the last subject has completed the 1-month follow up visit. The objective of the interim analysis is to assess the effectiveness and safety of each treatment group when all subjects complete Visit 3A (30-60 days post Visit 00A).

5 Safety Analysis Strategy

There are no safety hypotheses planned in this study. The focus of the safety analysis will be a comprehensive descriptive assessment of occurrence of adverse events as well as the other listed parameters.

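### Do the two day ranges given for Visit 3A (30-45 and 30-60 days after second-eye surgery) call for a change to the plan?

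*Protocol*

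**What the plan says.** Three places in current text give a day range for Visit 3A.

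- Protocol Table 3-1, the visit schedule: "Visit 3A Day 30-45 days Post Visit 00A".
- Protocol 12.7, on the interim analysis, which is to assess each group when "all subjects complete Visit 3A (30-60 days post Visit 00A").
- SAP 4.6, on the same interim analysis: "when all subjects complete Visit 3A (30-60 days post Visit 00A").

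Protocol 7.2 and SAP 1.5 speak only of the 1-month follow-up and give no days. SAP 1.2 states no window of its own; it says that the "schedule of study procedures and assessments are available in Table 3-1 of the protocol". Protocol 7.1 likewise sends the reader to the procedures table for the visit schedule.

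On handling, SAP 4.6 says "There will be an interim database lock" once the last subject has completed the 1-month visit. Protocol section 14 says "Deviations from this protocol, regulatory requirements and/or GCP must be recorded and reported to the Sponsor prior to database lock". Protocol 12.1 says "The final subject evaluability will be determined using the Deviations and Evaluability Plan (DEP) prior to locking the database". That plan (the DEP) is not among the documents.

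**The concern.** Read side by side, the texts treat a visit on day 50 after second-eye surgery in two ways: late under Table 3-1, on time under protocol 12.7. Deviations must be recorded before database lock, so two sites, or a site and its monitor, could each follow current protocol text and log the same visit differently. Visit 3A also carries the BCDVA measurement behind the 1-month interim summary, and its completion by all subjects leads to the interim lock.

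Three things might then be at stake: which records enter the 1-month summary, when the interim lock falls, and whether eyes leave the per-protocol set (PPS), which is the primary set for effectiveness.

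**Working it through.** **Size of the disagreement**

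Inputs: 30-45 days (Table 3-1); 30-60 days (protocol 12.7, SAP 4.6); Visit 4A at days 80-100 (Table 3-1); surgeries 7 to 14 days apart (protocol 7.1).

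- Table 3-1 range: 45 − 30 + 1 = 16 days.
- Interim-text range: 60 − 30 + 1 = 31 days.
- Days in the wider range only: 46 to 60, so 31 − 16 = 15 days. No day lies in the narrower range only.
- First eyes, counted from their own surgery: 30 + 7 = 37 to 45 + 14 = 59 days, against 37 to 60 + 14 = 74 days. Both ranges are anchored to Visit 00A and no first-eye window is stated, so this adds no separate conflict.

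**Can a record be assigned to the wrong visit?**

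Days strictly between the end of Visit 3A and the start of Visit 4A: 80 − 45 − 1 = 34 under Table 3-1, and 80 − 60 − 1 = 19 under the interim text. A record from days 46-60 is therefore nearer to Visit 3A than to any day that Visit 4A may occupy, except at the very end of the disputed span if distance is measured from day 45: day 60 is 15 days past 45 and 20 days short of 80, so even there Visit 3A is closer. Neither range overlaps Visit 4A.

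**Does either range select data?**

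The visible SAP text has no rule that drops out-of-window measurements or maps calendar days to visits. The interim summary is defined by the named visit. A day 50 examination entered as Visit 3A contributes to it under either text.

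**Does the lock date depend on the range?**

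The trigger is an event: the last subject completes the 1-month visit. Nothing visible stops a late visit from counting as completed. A delay of up to 60 − 45 = 15 days follows only if every subject is assumed to attend within window. Without that assumption, the lock follows the actual last visit under both texts.

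**Does a result depend on it?**

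The primary endpoint is the percentage of eyes with BCDVA of 20/20 or better at 6 months, which does not use Visit 3A. The interim tests nothing, and no design adaptation is expected from it. The sample-size figures depend only on the number of eyes and the observed percentage. For 63 of 90 eyes, the exact binomial interval is 59.4% to 79.2%, width 19.8%, as stated in protocol 12.8, and the visit window does not enter it.

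**Could the PPS be touched?**

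Only if the DEP grades a 1-month visit up to 15 days late as a major deviation. Even then the window belongs to the subject's visit and is anchored to Visit 00A. A timing exclusion would be expected to remove both eyes of that subject, one from each group.

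**The case for a change.** The strongest case for acting is that this is neither an extraction fault nor superseded text. The narrower range recurs in the repeated headers of Table 3-1, and the wider one appears in two separate documents, the SAP being written to the current protocol version. One could read 30-60 as a deliberately wider analysis window, but neither document says so, and if that was meant it should be labelled. Recording deviations is a duty, and a duty defined by two different ranges can be applied unevenly.

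What stands is that the mismatch exists and that a day 46-60 visit could be logged differently by different people. Beyond that, the case weakens:

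- Sites are directed to the schedule table for timing. Protocol 12.7 explains the aim of an analysis and does not tell sites when to see subjects.
- The SAP does not contradict itself separately. SAP 1.2 only points to Table 3-1, so this is the same discrepancy counted again.
- The ban on waivers ("Use of waivers to deviate from the clinical protocol is prohibited") is not engaged, because no waiver is proposed.
- The edit is small but not free. Section 4 requires an amendment for any protocol modification, and that covers the parenthesis in 12.7 as well as the table.
- The Manual of Procedures and the DEP may already settle how late visits are handled. Neither is available here.

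**Conclusion.** This is a clerical inconsistency between the schedule and the interim-analysis text, 15 days wide (days 46-60 after Visit 00A). The passages should be reconciled when the documents are next edited, either to one range or by labelling the wider one as an analysis window. Which range to keep is the sponsor's choice, and the documents do not determine it.

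It does not warrant a change to the plan in its own right, because there is nothing to gain in the analysis. The only effect shown is on how a visit in the disputed days might be logged. No effect is shown on the interim summary, the lock date, the PPS, the 6-month primary endpoint or the stated precision.

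This rests on three assumptions: that visits are analysed under their recorded visit name, that no unseen rule discards late 1-month data, and that the DEP does not treat such a visit as a major deviation. If the last were wrong, the number of eyes affected would be the number seen on days 46-60, which the documents do not give.
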